Management of Persistent Epistaxis Using Floseal Hemostatic Matrix

PROTOCOL IDENTIFYING NUMBER 001

PROTOCOL VERSION DATE June 8, 2015

GENERAL INFORMATION

Name and title of the investigators and sub-investigators responsible for the trial with address and phone numbers

[name] [name]

[name] [contact]

[name]

[name] [contact]

[name] BSc.

[name] [contact] [contact]

| Title | Management of Persistent Epistaxis using Floseal Hemostatic Matrix |
|--|---|
| Short Title | Floseal Epistaxis Study |
| Protocol Number | 001 |
| Phase | Phase 4 Clinical Trial |
| Methodology | Randomized open-label Trial |
| Study Duration | 1 Year |
| Study Center(s) | Single-Center, University of Alberta |
| Objectives | We wish to observe the effectiveness of Floseal Hemostatic Matrix in aborting persistent epistaxis with the end of bleeding being our primary outcome. We also wish to include measures of patient comfort and cost analysis of epistaxis treatment. |
| Number of Subjects | 60 |
| Diagnosis and Main Inclusion Criteria | Adult patients presenting for Otolaryngology Head and Neck Surgery consult in the Emergency Department with persistent epistaxis. |
| Study Product, Dose, | Floseal Hemostatic Matrix, 5mL |
| Duration of administration | 30 Minutes |
| Reference therapy | Standard nasal packing using gauze by a trained Otolaryngology resident |
| Statistical Methodology | This study is powered based on a non-inferiority analysis to compare the efficacy of Floseal at achieving hemostasis. We will perform standard chi-square statistical analysis to determine the significance of these outcomes. |

Study Summary

Table of Contents

| 1 | | BACKGROUND | .1 |
|----|-----|---|---------------------|
| | 1.1 | INVESTIGATIONAL AGENT | .1 |
| | 1.2 | PRECLINICAL DATA | .1 |
| | 1.3 | Risk/Benefits | .1 |
| | 1.4 | DOSE RATIONALE | .1 |
| | 1.5 | TRIAL CONDUCT | .1 |
| | 1.0 | POPULATION. | .2 |
| | 1./ | LII EKA I UKE | .2 |
| 2 | | TRIAL OBJECTIVES | .2 |
| 3 | | TRIAL DESIGN | .2 |
| | 3.1 | PRIMARY STUDY ENDPOINTS/SECONDARY ENDPOINTS | .2 |
| | 3.2 | Study Design/Type | .2 |
| | 3.3 | RANDOMIZATION | .3 |
| | 3.4 | TRIAL TREATMENT | .3 |
| | 3.5 | DURATION | .3 |
| | 3.6 | DISCONTINUATION | .4 |
| | 3.7 | DATA IDENTIFICATION | .4 |

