5.1 Efficacy Parameters

Efficacy of the Floseal Hemostatic Matrix will be determined by observing whether patients receiving either the Floseal or control treatment require additional measures to abort bleeding. Our primary endpoint is hemostasis, however if hemostasis is not adequately achieved, as determined by the OHNS resident providing direct care, than additional measures will be taken to abort bleeding and this will signify our primary endpoint.

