7.1 Statistical Methods

As this study is comparing a single experimental group to a control group we will use a standard statistical analysis to compare both the primary outcome of hemostasis and the secondary outcome results of the pain and comfort questionnaire. This is a non-inferiority study and has been powered as such. We will use a chi-square test to determine significance of any difference between the treatment and control group.

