7.3 Significance

This is a non-inferiority trial with a power of 0.8, a non-inferiority limit of 5% and a significance level of P < 0.05.

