Statistical Analysis Plan

Title of Study: Management of Persistent Epistaxis Using Floseal

Hemostatic Matrix

Protocol ID: 6601059

Date of Document: August 22, 2015

Date Modified: October 12, 2018

Sample Size:

An *a priori* sample size was calculated using a non-inferiority limit (d) set at 25%, significance level (α) of 5% and power of 80%. We assumed that success in each group will be approximately 93% based on the literature examining anterior nasal packing in ideal conditions and considering our selection criteria in the Floseal® (Baxter, USA) population. Attrition will be assumed to be 0% due to the short duration of treatment. This should yield 26 participants with 13 patients in each study arm.

Statistical Analysis of Clinical End-points:

This is a non-inferiority trial. A non-inferiority design was chosen due to the anticipated improvement in patient comfort and potential decreased cost thus making the experimental arm a preferred option if non-inferiority can be demonstrated in terms of hemostasis. Further, based on existing literature we do not anticipate a significant difference in terms of efficacy between these two groups. All dichotomous categorical variables will be analyzed by means of the Fisher's exact test. Mean age, CCI and VAS pain scores will be compared using the non- parametric Mann-Whitney U Test.

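### The trial is declared non-inferiority, but hemostasis is tested only for zero difference, so nothing short of superiority can establish non-inferiority

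*SAP*

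**What the plan says.** Protocol 7.1, 7.2 and 7.3 and the SAP all call this a non-inferiority trial. Protocol 5.1 makes hemostasis a yes/no outcome by "observing whether patients receiving either the Floseal or control treatment require additional measures to abort bleeding". The SAP's sample-size paragraph does the same: "We assumed that success in each group will be approximately 93" per cent. (Protocol 3.1 words the endpoint as the moment bleeding stops, but no time-to-event analysis follows.)

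The tests that cover hemostasis are:

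- Protocol, Study Summary: "We will perform standard chi-square statistical analysis to determine the significance of these outcomes".
- Protocol 7.1: "We will use a chi-square test to determine significance of any difference between the treatment and control group".
- SAP, Statistical Analysis of Clinical End-points: "All dichotomous categorical variables will be analyzed by means of the Fisher's exact test". This sentence does not name hemostasis but covers it as a dichotomous variable.

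The margin appears in two places. Protocol 7.3 gives "a non-inferiority limit of 5% and a significance level of P < 0.05". The SAP gives 25% as an input to its sample size. Neither place names a test or interval to be compared with the margin, and neither states whether the level is one- or two-sided.

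The SAP makes its conclusion depend on the missing step, "thus making the experimental arm a preferred option if non-inferiority can be demonstrated in terms of hemostasis", and adds that "we do not anticipate a significant difference in terms of efficacy between these two groups".

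**The concern.** As ordinarily used, chi-square and Fisher's exact test ask whether the two success rates are equal. Non-inferiority asks whether Floseal could be worse than packing by as much as the margin. A significant difference in favour of Floseal would answer both questions. A non-significant difference answers neither, because with few patients it is compatible with a large deficit.

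The SAP chose this design partly because it expects similar efficacy, so a non-significant Fisher result is the likely outcome. The named tests cannot turn that result into the conclusion the trial exists to reach. The interval method, the sidedness and the reading of the margin would then have to be settled outside the written plan, possibly with the data in view.

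**Working it through.** **Inputs.** SAP: 13 per arm, 93% success in each arm, margin 25% (taken as an absolute difference in percentage points), α 5%, power 80%, no attrition. Protocol: 30 per arm, margin 5%, P < 0.05, power 0.8, no success rate stated.

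**The SAP's sample size reproduces.** With the unpooled normal approximation,

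n per arm = (z₁₋α + z₁₋β)² × 2p(1−p) / d² = (1.645 + 0.842)² × 2 × 0.93 × 0.07 / 0.25² = 12.9, so 13 per arm and 26 in total.

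This requires one-sided 5%; one-sided 2.5% gives 17 per arm. The trial was therefore sized for a margin-based test that its analysis section does not contain.

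**What Fisher can deliver at 13 per arm.** If Floseal succeeds in 13/13 and packing in 8/13, two-sided p = 2 × C(13,5)/C(26,5) = 2 × 1287/65780 = 0.039. With packing at 9/13, p = 2 × C(13,4)/C(26,4) = 2 × 715/14950 = 0.096. Two-sided significance in favour of Floseal is therefore impossible unless packing succeeds in 8/13 or fewer.

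Summing binomial probabilities over all 14 × 14 possible tables, with equal true rates:

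| True success, both arms | Fisher significant for Floseal, two-sided 5% | One-sided 5% |
|---|---|---|
| 90% | 0.17% | 0.9% |
| 93% (SAP) | 0.05% | 0.4% |
| 95% | 0.01% | 0.16% |

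At 93% in both arms, two-sided Fisher is non-significant in 99.9% of trials.

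**What a margin-based rule would deliver.** The rule is that the lower limit of the two-sided 90% interval for Floseal minus packing lies above −25 points. The enumeration is the same; the margin case is 93% − 25 points = 68% for Floseal.

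| Method | Shows non-inferiority, 93% v 93% | Fisher non-significant and non-inferiority not shown, 93% v 93% | False claim, 68% v 93% | Largest false-claim rate over all pairs 25 points apart |
|---|---|---|---|---|
| Score (Farrington-Manning) | 63% | 37% | 4.0% | 6.6% |
| Newcombe | 66% | 34% | 6.0% | 6.6% |
| Wald | 81% | 19% | 7.6% | 12.7% |

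An exact unconditional test ordered by the score statistic also gives 63% at 93% v 93%, and holds the false-claim rate at or below 5% by construction.

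**Two possible results.**

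- Floseal 11/13, packing 13/13. Fisher p = 2 × C(13,2)/C(26,2) = 2 × 78/325 = 0.48. Wald lower limit: −0.154 − 1.645 × √(0.846 × 0.154/13) = −31.8 points. Score and Newcombe: −37.5. The Fisher result is unremarkable, yet every interval crosses −25.
- Floseal 12/13, packing 13/13. Fisher p = 1.0. Wald: −0.077 − 1.645 × √(0.923 × 0.077/13) = −19.8 points, which passes. Score and Newcombe: −28.2, which fail. A single failure leaves the verdict to a method the plan does not name.

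**If non-significance were read as non-inferiority.** Neither document says this. If it were done, a Floseal truly worse by the full margin (68% v 93%) would pass in 80% of trials.

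**The protocol's design.** At 30 per arm, with equal success assumed at 80% to 95% because the protocol gives no rate, uncorrected chi-square is significant in favour of Floseal in 1.4% to 2.7% of trials. The problem is not peculiar to the smaller sample size.

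**The case against.** The best defence is that the rule can be inferred. Protocol 7.3 puts the limit and the significance level in one sentence, and the SAP's 13 per arm reproduces only at one-sided 5% against 25 points. A reader could reconstruct a comparison with −25 points at that level, so the freedom left is narrower than complete absence of a rule suggests. That is fair as far as it goes. However, Protocol 7.1 says its test is for any difference, the two documents give different margins, and no interval method can be inferred from either. The 12/13 v 13/13 case shows that the method alone can change the verdict.

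The Fisher sentence may also be only a general statement, with the primary analysis left out. In that case the SAP names no primary analysis at all, and the chi-square in Protocol 7.1, which does cover hemostasis expressly, remains. Likewise, the SAP's remark about not anticipating a difference gives a reason for the design; it does not say how a p-value would be read. That is correct, and the finding does not need it to say more.

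The 80% false-claim figure describes a misuse the documents do not endorse. It illustrates the risk and should not carry the argument.

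Finally, score and Newcombe intervals can themselves exceed 5% (up to 6.6%). This stands: they are clearly better than Wald (up to 12.7%), but only an exact unconditional method guarantees the level.

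**Conclusion.** The concern holds and must be fixed. Followed as written, the plan can support non-inferiority only by showing superiority. At 13 per arm and 93% success in both arms, that has a probability of 0.05% (two-sided) or 0.4% (one-sided). A margin-based rule would reach the conclusion in 63% to 81% of the same trials, depending on the interval.

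These figures assume the SAP's success rate, an absolute 25-point margin, one-sided 5% (which the SAP does not state but its sample size implies) and complete data. Changing the common success rate to 90% or 95% leaves the two-sided Fisher probability below 0.2%. That the named tests do not address the margin depends on none of these assumptions.

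**What to change.** Define the primary analysis as the difference, Floseal minus packing, in the proportion achieving hemostasis without additional measures. Prespecify one small-sample interval and its one-sided level; 5% is the level that matches the SAP's sample size. An exact unconditional interval guarantees the level; Farrington-Manning score and Newcombe are workable alternatives if a small excess over nominal is accepted and stated. Do not use Wald. Conclude non-inferiority only if the lower limit lies above minus the margin, and say that a non-significant difference test is not evidence of non-inferiority. Keep Fisher's exact test for the other dichotomous variables.

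The 5% and 25% margins must first be reconciled, and the Study Summary, Protocol 7.1 and 7.3 and the SAP brought into line. Protocol 7.5 already requires statistical changes to be amended and justified in the protocol.

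The rule itself needs no new data or visits, but it has a cost in power. At 13 per arm, 93% in both arms and a 25-point margin, the stated 80% becomes about 63% (score or exact unconditional) or 66% (Newcombe). Keeping 80% with one of these methods means enrolling more than 13 per arm. If the 5% margin were kept, the same sizing formula gives (1.645 + 0.842)² × 2 × 0.93 × 0.07 / 0.05² = 322 per arm, borrowing the SAP's 93% because the protocol states no rate.
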